### **Study Design**

A three-arm quasi-experimental trial involving: 1. co-developed physical activity referral scheme (intervention); 2. standard ERS (usual care); and 3. no treatment control. Process evaluation will be embedded to establish reach, adherence, fidelity and acceptability of the intervention and usual care conditions.

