## Sample size estimation

### *Between-group effects (intervention vs usual care)*

Required sample size was estimated by using effect sizes of a previous pilot study that demonstrated a mean change in CRF  $3.6 \pm 3.2 \text{ ml.kg.min}^{-2}$  (REF 16/WA/0231) and existing epidemiological evidence. A change in cardiorespiratory fitness of  $3.5 \text{ ml.kg.min}^{-2}$  has been deemed clinically meaningful with an associated reduction in all-cause mortality (13%) and cardiovascular disease risk (15%; Lee et al., 2010). Yet, it has also been demonstrated that small increases in fitness (Males:  $0.5 \text{ ml.kg.min}^{-2}$ ; Females  $1.0 \text{ ml.kg.min}^{-2}$ ) are associated with significant reductions in clustered-cardiometabolic risk in at-risk individuals (Simmons et al., 2008).

Therefore, we decided a moderate-large effect size (based on pilot baseline CRF SD of  $3.2 \text{ ml.kg.min}^{-2}$  equivalent to a change of  $1.98 \text{ ml.kg.min}^{-2}$ , would be clinically meaningful. This is between the clinically meaningful change of 3.5 units reported by Lee et al. (2010) and the smaller increases of 0.5 to 1 unit reported by Simmons et al. (2008) in at-risk individuals. Thus, to detect a difference of 1.98 units ( $\text{ml.kg.min}^{-2}$ ) between groups, it was estimated that a total sample of 84 would be needed ( $f=0.25$ ,  $p=0.05$ , power = 0.8). Factoring for dropout witnessed in the pilot study (40%) this yields a sample of 140 patients (70 per ERS arm).

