### **Outcome measures**

aAll patient outcome data will be collected at two time-points: pre-intervention (prior to an induction with an ERP) and at Week 12 (post 12-week consultation with an ERP). bAt 6-month follow-up, **questionnaire-based measures and PA levels** (determined by an accelerometer worn for 7 days), **only** will be collected. All data will be collected and analysed by a researcher at LJMU. All outcome measures were piloted in a previous study (REF 16/WA/0231) and were deemed acceptable by patients and demonstrated adequate sensitivity to detect change.

a Collected at Baseline and week 12

b Collected at Baseline, week 12 and 6-month follow-up

a **Cardiorespiratory Fitness.** A sub-maximal VO2 test (Astrand Rhyming test) will be carried out to estimate cardiorespiratory fitness. The Astrand Rhyming test allows you to predict VO2max from work intensity and heart rate. Following a warm-up (unloaded cycling 3-5 minutes at 50-60 rpm) the procedure will begin. Using a Polar Heart Rate Monitor to measure heart rate, the individual will begin cycling at 60 rpm with a workload of 60 watts (female) or 90 watts (male). The participant will then cycle at this workload for 6 minutes. Heart rate will be measured each minute; blood pressure will be measured at each 3-minute period as well as pre- and post-test. If the mean heart rate is between 125 and 170 beats per minute at minute 5 and 6, the test can be terminated. If the mean heart rate is less than 125 beats per minute, the workload will be increased by 30 watts (0.5 kg). If the mean heart rate is less than 125 beats per minute at minute 5 and 6 the test will be continued for a further 3 minutes. This procedure will be repeated until the required heart rate is achieved. The test will be stopped if the participant experiences any adverse effects, their heart rate exceeds recommended max heart rate values for this test, or if the participant wants to stop.

b **Objective PA levels.** Objective PA will be analysed using an accelerometer (ActiGraph software), which will be fitted during baseline testing at LJMU. A baseline 7-day monitoring period will occur before participants engage with the scheme. During the 7-day monitoring period, each participant will complete a diary to record hours of use as well as distinguish between work and leisure hours.

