**Analyses**

Statistical analysis of the primary and secondary outcomes will be conducted using linear mixed models in SPSS Statistics Version 23 (SPSS Inc., IBM Corp., Armonk, NY), with alpha levels set at  $P < .05$ . The models will be used to assess the impact of treatment (co-developed ERS, usual care ERS, and no treatment control), time (baseline and post-tests), and Group  $\times$  Time interactions. Mixed models are robust to the biases of missing data and provide appropriate balance of Type 1 and Type 2 errors. Mixed-model analyses are consistent with the intention-to-treat principle, assuming the data are missing at random. Appropriate variables including baseline values will be included as covariates in the models. The data will be screened for skewness and kurtosis prior to commencing any analyses. Magnitude-based inferences will be used to investigate 'clinical meaningfulness' of results (Batterham and Hopkins 2006).

Focus groups and interviews will be recorded and transcribed verbatim (where they will be anonymised). They will then be analysed using NVivo electronic software using a thematic approach to allow common themes to arise from the data collected. Members of the research team will review the data independently and meet to reflect on the emerging themes, discuss rationale for coding decisions, areas of disagreement and theoretical concepts that emerge.

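### The outcome's baseline is used both as a time level and as a covariate; for two-visit fitness under a random-intercept fit, type I error is about 13–14% at the planned 40% dropout

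*Combined protocol and SAP*

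**What the plan says.** The Analyses section states that the primary and secondary outcomes "will be conducted using linear mixed models in SPSS Statistics Version 23". It continues: "The models will be used to assess the impact of treatment (co-developed ERS, usual care ERS, and no treatment control), time (baseline and post-tests"), followed by Group × Time interactions. Baseline is therefore a level of the time factor, and the baseline measurement is a response. The same paragraph then says: "Appropriate variables including baseline values will be included as covariates in the models". No random-effects or residual covariance structure is given, and nothing limits either role of baseline.

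Under Outcome measures, CRF carries the footnote "Collected at Baseline and week 12", so it has two visits only. The sample size section expects heavy loss: "Factoring for dropout witnessed in the pilot study (40%) this yields a sample of 140 patients (70 per ERS arm"). The Analyses section keeps incomplete patients through the mixed model under a missing-at-random assumption and says: "Mixed models are robust to the biases of missing data and provide appropriate balance of Type 1 and Type 2 errors". The Study Design section describes "A three-arm quasi-experimental trial involving" two exercise referral arms and an untreated control, so the arms are not randomised.

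**The concern.** Each role of baseline is legitimate alone. Together they make the baseline row a response that is predicted by itself. Three things follow for a two-visit outcome.

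- With complete data the Group × Time estimate is exactly the difference in mean change scores. The covariate gives no regression adjustment for baseline.
- The covariate makes a person's two residuals negatively correlated. A random-intercept variance cannot be negative, so it is estimated at zero and the two rows are treated as independent.
- Patients who drop out after baseline contribute only a self-predicted row. Its small residual lowers the pooled residual variance but tells us almost nothing about week 12.

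At stake is whether the test of co-developed scheme against usual care holds its 5% level, which the plan's remark on Type 1 and Type 2 errors takes for granted. There is also a question of estimand. With non-randomised arms, change-score and baseline-adjusted analyses answer different questions, and the plan does not choose between them.

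**Working it through.** **1. The plan's own figures.** Inputs from the sample size section: difference 1.98, SD 3.2, alpha 0.05 (two-sided assumed), power 0.8, dropout 40%.

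n per arm = 2 × (1.96 + 0.842)² × (3.2/1.98)² = 2 × 7.85 × 2.612 = 41.0. The value is just above 41, so it rounds up to 42, and an exact t calculation also gives 42. Total 84; 84/0.6 = 140, or 70 per arm. The figures reproduce from 1.98/3.2. (The quoted f = 0.25 would instead need 64 per arm; that does not affect this point.) The expected data are thus 42 patients per ERS arm with both visits and 28 with baseline only.

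**2. Closed form for the random-intercept fit.** Assumptions: no true effect, variance 1 at both visits, baseline to week-12 correlation r (the documents give none), dropout completely at random. Let p be the proportion with a week-12 value.

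- Pooled baseline slope: β = (1 + pr)/(1 + p).
- Completers' residual covariance: (1 − β)(r − β) = −p(1 − r)²/(1 + p)². This is negative for every r below 1, so the intercept variance goes to zero and the fit becomes ordinary least squares on pooled rows.
- Residual variance: s² = [(1 − β)² + p(1 + β² − 2βr)]/(1 + p).
- Model variance of the interaction (per arm, times n): s²(1 + 1/p).
- True variance on the same scale: (1 + k² − 2kr)/p + (1 − p)(1 − β)², with k = 1 − (1 − p)(1 − β).
- Type I error: 2[1 − Φ(1.96 × SE ratio)].

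With complete data (p = 1) the SE ratio reduces to √((3 + r)/4).

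| Dropout | r | β | Model variance | True variance | SE ratio | Type I error |
|---|---|---|---|---|---|---|
| 0% | 0.3 | 0.650 | 1.155 | 1.400 | 0.908 | 7.5% |
| 0% | 0.5 | 0.750 | 0.875 | 1.000 | 0.935 | 6.7% |
| 0% | 0.7 | 0.850 | 0.555 | 0.600 | 0.962 | 5.9% |
| 40% | 0.3 | 0.738 | 1.216 | 2.134 | 0.755 | 13.9% |
| 40% | 0.5 | 0.813 | 0.906 | 1.565 | 0.761 | 13.6% |
| 40% | 0.7 | 0.888 | 0.566 | 0.963 | 0.767 | 13.3% |

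At 20% dropout the same formulas give 9.9 / 9.3 / 8.7%.

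**3. Simulation.** REML fits of group, time, Group × Time, baseline covariate and random intercept, two ERS arms, 4,000 runs per setting, r = 0.3 / 0.5 / 0.7. The intercept variance was zero in at least 99.5% of runs.

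- Complete data, 42 per arm: 7.4 / 6.7 / 6.5%. The interaction equalled the change-score difference in every run.
- 70 per arm with 40% dropout and baseline rows kept: 14.1 / 13.9 / 14.6%, with the SE at 75 / 76 / 75% of its true value.

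A separate simulation with all three arms (70/70/30, 40% dropout, 3,000 runs, r = 0.5 to 0.9) gave 13.0–13.8% for intervention against usual care and 17–18% for the three-arm Group × Time test.

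**4. Other covariance structures, two visits.**

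- Negative covariance allowed: 5.0 / 5.0 / 5.6% with complete data, but 11.4 / 12.3 / 13.3% with 40% dropout.
- Unstructured: no proper fit, because a slope of 1 leaves zero residual at baseline.

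**5. Three-visit outcomes, random intercept** (2,000 runs): 4.6 / 6.3 / 5.2% with complete data; 7.9 / 8.5 / 9.6% with 40% dropout.

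**6. Baseline in one role only, CRF, 40% dropout.** ANCOVA of week 12: 5.0 / 4.8 / 5.1%. Group × Time without the baseline covariate: 5.1 / 4.8 / 5.3%.

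**7. Estimand.** If the arms differ at baseline by a stable amount d, the change-score estimate has expectation 0 and ANCOVA has d − rd = (1 − r)d. For an assumed d of 1 unit that is 0.7 / 0.5 / 0.3 units. Divided by 1.98, this is 35 / 25 / 15% of the target difference.

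**The case against.** The strongest reply is that the text is loose and does not fix a model. The baseline values could be those of other variables, such as the demographics collected at baseline, or the analyst could fit post-test rows only. The covariance structure is unstated, so the plan implies no single error rate. An unstructured fit would fail visibly and might alert the analyst. The 14% also needs retained baseline-only rows and the full 40% dropout, which is a planning value from the pilot; with complete data the inflation is modest or absent.

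Part of this stands. The figure is conditional on the reading, the covariance structure and the dropout, and should be quoted with its range. The complete three-visit results show no consistent problem, although 6.3% at r = 0.5 is somewhat more than Monte Carlo error of about 0.5 points explains. The 14.6% at r = 0.7 is above the closed form, so 13–14% is the better summary. The choice between change score and ANCOVA is separate from type I error.

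The objection does not remove the point. The outcome's own baseline is the natural reading, and nothing in the documents excludes it. The dropout figure is the plan's own. Neither covariance structure that gives a usable two-visit fit holds 5% at that dropout. Letting the baseline slope differ by visit does not help either, because it would fit the baseline rows exactly.

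**Conclusion.** The concern holds: the analysis is wrong as written and must be fixed. If the outcome's baseline is both a time level and a covariate, the CRF comparison of the two ERS arms has a standard error about 75–77% of its true value, and type I error of about 13–14%, at 40% dropout under a random intercept. It is 8.7–9.9% at 20% dropout and 5.9–7.5% with complete data. With negative covariance allowed it is about 5% with complete data and about 11–13% at 40% dropout.

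These results assume equal variances, dropout completely at random, and a correlation the documents do not supply. The 40% result barely depends on that correlation. Confidence is medium, because the reading and the covariance structure have to be inferred. No loss of power against the plan's 1.98-unit target is claimed.

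**What to change.** Give the outcome's baseline a single role and state the covariance structure. There are two sound options.

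- **(a) Baseline as covariate only.** The responses are post-baseline values. For CRF this is ANCOVA of week 12. For three-visit measures, model week 12 and 6 months with group × visit, baseline × visit and unstructured covariance.
- **(b) Baseline as a time level only.** Keep Group × Time as the test and remove the outcome's own baseline from the covariates. Other baseline variables may stay.

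The arms are not randomised, so (a) and (b) rest on different assumptions when they differ at baseline. Pre-specify one as primary, justify it, and report the other as a sensitivity analysis. The cost is one paragraph of analysis wording and one additional analysis, with the same data and software.

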### **Objectives:**

- To investigate the relative effectiveness (for improving cardiorespiratory fitness at 12 weeks) and cost-effectiveness (PA levels at 6 months) of two delivery modes of ERS (1. co-developed physical activity referral scheme; 2. standard ERS)
- To explore who each intervention reaches, patient adherence levels, fidelity of intervention delivery and acceptability of the intervention to patients and staff.

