## Recruitment

### ***Intervention and usual care conditions***

Eligible patients will be recruited from Centre A and Centre B (after they have been referred to the ERS by a health professional). Once referred, it is standard protocol that ERS patients visit their chosen *Lifestyles* fitness centre to book an ERS induction with administrative staff. During this initial contact, administrative staff will introduce the study briefly and provide the individual with a summary poster (attached). If the patient is interested, administrative staff will gain verbal consent to pass the patient's contact details to the researcher (NB this is consent for sharing details only, the participant will still have the opportunity to opt out before full research consent is sought). Administrative staff will then provide patients with the participant information sheet to take away and have some time to consider. Patients will be informed that the researcher will contact them within one week to discuss the study and check if they want to take part. Researcher contact details will be provided on the poster and information sheet in case the participant has any questions in the meantime.

For patients who consent to speak to the researcher, the administrative staff will book an ERS induction 2-3 weeks later (to allow time for the patient to undergo baseline testing prior to starting the ERS). The researcher will then contact the patient to arrange a visit to Liverpool John Moores University (LJMU) laboratories for baseline collection of health measures.

Patients who opt out of the study at this stage will continue with the ERS as usual.

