#### ***No treatment control condition***

Participants in the no treatment control group will be recruited via posters placed around LJMU, electronic invitations on LJMU research recruitment websites, email communications to LJMU staff and students, and LJMU social media output (see attached documents). Interested participants will contact the researcher for further information, who will e-mail them a full participant information sheet. If the participant then decides to take part the researcher will arrange a date and time to visit LJMU laboratories for baseline collection of health measures.

**Participant blinding.** Due to the nature of the study, it will not be possible to fully blind patients to their study condition (as they will know whether they are signed up to attend an ERS or not) or to blind ERS staff (who will know whether their centre is the intervention or the usual care condition). Patients within the two active conditions (intervention and usual care) will not however be informed whether their centre is the intervention or the usual care condition.

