## **Measures**

### **Demographic measures**

Demographic measures collected at baseline will include: date of birth, sex, postcode, employment status, ethnicity, referral reason, referring professional, and number of previous referrals.

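### As the mixed model is written, baseline is an outcome row and covariates are simply added, so the planned adjustment gives no useful control of confounding in the Group × Time effect

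*Combined protocol and SAP*

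**What the plan says.** Study Design describes "A three-arm quasi-experimental trial". Under Recruitment, the two exercise referral scheme (ERS) arms are formed by centre ("Eligible patients will be recruited from Centre A and Centre B"), and patients go to a fitness centre of their own choosing. The controls come from elsewhere: they "will be recruited via posters placed around LJMU" or answer university emails and social media. The clinical effectiveness objective is stated as "for improving cardiorespiratory fitness at 12 weeks", and cardiorespiratory fitness (CRF) is measured twice, at baseline and at week 12.

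The Analyses section specifies linear mixed models with treatment, time and their interaction. The levels of time are "time (baseline and post-tests"), so the baseline value is part of the outcome. On covariates it says only: "Appropriate variables including baseline values will be included as covariates in the models". It names no covariate other than baseline values, gives no covariate × time term, and does not say which coefficient is the primary estimate. No matching, weighting or propensity score is described. Demographic measures lists what could serve as covariates: date of birth, sex, postcode, employment, ethnicity, referral reason, referring professional and "number of previous referrals".

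**The concern.** With two visits and baseline as a level of time, the Group × Time coefficient is the between-arm difference in change from baseline. A covariate that is fixed for each patient and carries one coefficient has no route into that quantity. The trial could therefore report an effect described as adjusted for age, sex, referral reason and so on that is, in substance, the crude difference in mean change.

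This matters because nothing is randomised. If patients at the two centres differ in characteristics that predict how much fitness changes over 12 weeks, the comparison of the co-developed scheme with standard ERS is biased. The only adjustment the plan names would not remove that bias.

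**Working it through.** **1. The plan's own sample size.** Inputs from Sample size estimation: difference 1.98, SD 3.2, alpha 0.05 (taken as two-sided), power 0.8. Per arm, 2 × (1.960 + 0.842)² × (3.2/1.98)² = 41.002, rounded up to 42. That is 84 in total, and 84/0.6 = 140. The plan's 84 and 140 are reproduced. They follow from 1.98/3.2 = 0.619, not from the printed f = 0.25, which needs 128; that is a separate matter. Only 42 evaluable per arm, SD 3.2 and 40% dropout are carried forward.

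**2. Algebra.** For patient i in arm g with covariate x:

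- baseline: Y₀ = a + b·g + c·x + e₀
- week 12: Y₁ = a + b·g + d + θ·g + c·x + e₁
- change: Y₁ − Y₀ = d + θ·g + (e₁ − e₀)

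The term c·x is gone, so θ, the Group × Time effect, is the raw difference in mean change whatever x is. The same holds when x is the baseline value. If x is also given a time interaction h·x in the week-12 row, the change becomes d + θ·g + h·x + error, and θ is then adjusted for x.

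**3. Simulation.** These assumptions are not in the documents: one covariate differing by 0.5 SD between the ERS arms, shifting CRF change by 1 unit per SD; true effect 1.98; 70, 70 and 30 patients.

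| Model | One complete data set: estimate | 40% dropout, missing at random, 700 runs: bias |
|---|---|---|
| Group × Time, no covariate | 3.308218 | +0.38 |
| plus covariate main effect | 3.308218 | +0.40 |
| plus covariate and baseline CRF main effects | 3.308218 | +0.44 |
| plus covariate × time | 2.984 | −0.03 |
| week-12 value on arm, baseline CRF and covariate | 2.887 | −0.03 |

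The first three complete-data estimates equal the raw difference in change. Monte Carlo error on the no-covariate bias is about 0.70/√700 = 0.03, and it is similar for the other rows. With dropout, patients seen only at baseline contribute between-patient information, so the estimate does move: by 0.07 to 0.08 units on average with the covariate, and by 0.12 with baseline added (largest single shift 0.45). The bias did not fall.

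One further result concerns baseline CRF as both outcome and covariate in a random-intercept model. With 40% dropout its average model standard error was 0.50, against an actual spread of estimates of 0.69. Confidence intervals would be too narrow.

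**4. Size of the bias.** Assume no true effect and a change SD of 3.2. Bias = imbalance in SDs × correlation with change × 3.2. The standard error is 3.2 × √(2/42) = 0.698. Type I error is from the noncentral t on 82 degrees of freedom, with noncentrality bias/0.698.

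| Imbalance (SD) | Correlation | Bias (units) | Share of 1.98 | Noncentrality | Type I error |
|---|---|---|---|---|---|
| 0.3 | 0.2 | 0.19 | 10% | 0.27 | 6% |
| 0.5 | 0.3 | 0.48 | 24% | 0.69 | 10% |
| 0.8 | 0.5 | 1.28 | 65% | 1.83 | 44% |

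**The case against.** Five objections deserve an answer.

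- **The plan does not say main effects.** This is correct. The text is silent on interactions, and naming baseline values as a covariate may signal an intended baseline-adjusted model of the post-test values, which would adjust properly. That intention would conflict with listing baseline as a level of time, so the passage needs rewriting on either reading.
- **A reader might infer that covariates can never change the estimate.** That is exact only for complete data. With the planned dropout the estimate shifts a little. What stands is that the shift did not reduce the bias.
- **A reader might infer that the analysis has no protection at all against confounding.** The documents do not support that. A contrast of change removes stable additive differences in level between centres. Confounding of change, and regression to the mean, remain.
- **A reader might infer that every control row would be lost, because referral variables do not exist for people recruited by advertisement.** The plan does not name those variables as covariates or say how they would be coded for controls. A count of previous referrals can be recorded for anyone. It is a reason for care in choosing covariates, not an established fault.
- **The week-12 model is not automatically the better remedy.** This stands. If the arms differ stably in true fitness and baseline CRF is measured with error, adjusting for the observed baseline leaves a bias of gap × (1 − reliability). For an assumed gap of 1.6 units (0.5 × 3.2), that is 0.16, 0.32 and 0.48 at reliability 0.9, 0.8 and 0.7, while the change contrast is unbiased in that setting. CRF here is predicted from a submaximal test, so measurement error is plausible. The simulation above used a single perfectly measured confounder and could not show this.

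**Conclusion.** The concern holds in this form: read in its ordinary sense, the stated model yields an estimate that is adjusted in name while confounding of change by case mix stays uncontrolled. The cancellation is algebra and needs no assumption about effect size. That dropout does not rescue the adjustment rests on simulation under data missing at random.

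The illustrative size, 0.48 units with type I error of about 10%, rests on an assumed imbalance of 0.5 SD and correlation of 0.3. Over the range shown it runs from 0.19 to 1.28 units and from 6% to 44%. Those inputs have no source in the documents, so the range shows what could happen and does not predict this trial's bias. The SD is an approximation too: the plan attaches 3.2 both to pilot change and to pilot baseline CRF.

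This is more than missing detail, because it affects the 12-week CRF comparison in a design where covariates are the only adjustment named.

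**What to change.** Rewrite the covariate sentence in Analyses as follows.

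1. Keep the repeated-measures model with baseline as a level of time, and remove baseline CRF from the covariates.
2. For co-developed versus standard ERS, name a short list of baseline covariates already being collected, for example age, sex, employment, referral reason and number of previous referrals. Enter each with its covariate × time interaction. State that the adjusted Group × Time coefficient at week 12 is the primary estimate.
3. Report a week-12 model adjusted for baseline CRF and the same covariates as a sensitivity analysis, or name it as primary before the data are seen. The two models rest on different assumptions in non-equivalent groups, so the choice should not follow the results.
4. For contrasts with the no-treatment control, use only covariates defined in all three arms.

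The cost is wording and a few degrees of freedom out of about 84 evaluable patients; no new data are needed. If employment and referral reason were each collapsed to three categories, the interactions would number 1 + 1 + 2 + 2 + 1 = 7, leaving about 82 − 7 = 75 degrees of freedom for the change contrast. The grouping of multi-category variables should therefore be fixed in advance and kept coarse.
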